## **Interim analyses**

An interim analysis will be conducted bi-monthly by study analysts once data collection starts. This will include the development of syntax to clean the data (e.g., missingness analysis, identification of data entry errors, recoding variables). The key variables will be reviewed. Descriptive data will be presented to PIs and members of the NCCB. The NCCB will review preliminary findings presented by the PIs on a bi-monthly basis to address any potential adverse reactions that may occur and any safety concerns that may arise. If any participants are found to be unresponsive to the intervention, or getting worse during the course of the study, an NCCB sub-committee will discuss the case and the participant may be terminated from the study and referred to relevant services in the community. The PIs will meet weekly with the study staff to review the study protocol adherence and address any potential problems. The PIs will also have weekly supervision meetings with intervention facilitators to review the results from fidelity ratings and address any potential deviance from interventions.

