## **Statistical Analysis Plan**

Data analysis: Aim 1. We will estimate the (1) differences in the effects of first-stage interventions (NS vs brochure), (2) differences in the effects of second-stage interventions (BC vs NS among those who complete testing and referral vs CD among testing decliners), and (3) differences in the effects of selected adaptive interventions on acceptance of testing and adherence to NJ recommendations. For the differences between NS and brochure, cross-tabulations of the interventions with each outcome will be generated, and crude odds ratios comparing the two will be calculated. For the effects of second-stage and third-stage interventions, we will perform a similar analysis as that for the first-stage interventions but on corresponding subsets as indicated in the specific comparison groups. The estimation of effects of embedded adaptive interventions will use weighted and replicated estimation techniques. Under these procedures, the data set will be restructured wherein an individual's outcome will be replicated in the data set depending on the number of adaptive interventions consistent with this outcome. Since randomization at both stages is based on equal probabilities, weighting is not necessary. The restructuring of the data set as described allows the utilization of standard statistical software for parameter estimation and hypothesis testing. A generalized linear model using logistic regression will be performed where estimation of model parameters will be done using generalized estimating equations due to the presence of replicated subjects. We will then use tests of contrasts to compare selected adaptive interventions. The analysis of the adaptive interventions will be done using PROC GENMOD in SAS. To adjust for baseline characteristics and test for their moderating effects, we will incorporate these terms and their interactions with first-stage, second-stage, and adaptive interventions in their respective models. Only the baseline characteristics will be used for adjustment, as outcomes of the first-stage intervention are biased if incorporated into this model. Odds ratios, 95% CI, and Wald's test for the effect of interventions and covariates will be obtained from these results. Sex/gender and race/ ethnicity will be among these covariates that we will consider for adjustment and moderation analysis.

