**Methods in analysis to handle protocol non-adherence and any statistical methods to handle missing data**

We will perform an intent-to-treat analysis of the data. Subjects will be grouped according to how they are randomized. The multiple imputation strategy described will be adapted [43]. This uses a time-ordered nested conditional imputation strategy with multiple imputation of missing values. In this approach, the fully conditional specification (FCS) imputation framework wherein a separate model for each variable is fitted will be applied. We will consider the time ordering of the data. For example, observed baseline variables will be used to impute for missing data from the first-stage results. Then, the imputed and observed values of the first-stage results will be used in conjunction with baseline variables to impute missing values for the second-stage results. We will examine the distribution of missing data according to intervention groups, covariates (e.g., demographic characteristics, adherence, reason for discontinuation), outcome variables, and time. We will determine whether the missing data pattern is not inconsistent with the missing-at-random (MAR) mechanism. We will also check whether the amount of missingness is monotonic over time. The R software packages mice and pan will be used for imputation.

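### The SAP allows unresponsive or worsening participants to be removed from the study itself, and no text available says their scheduled outcomes are still collected

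*SAP*

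**What the plan says.** The SAP's Interim analyses section sets up a recurring review: "The NCCB will review preliminary findings presented by the PIs on a bi-monthly basis", and the stated purpose is "to address any potential adverse reactions that may occur and any safety concerns that may arise". The same paragraph goes beyond safety. It covers the case "If any participants are found to be unresponsive to the intervention, or getting worse during the course of the study"; the sub-committee then discusses the participant, and "the participant may be terminated from the study and referred to relevant services in the community". The text does not say who takes the final decision or what counts as non-response.

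The protocol's section 8 (Confidentiality of data) gives the general schedule of a baseline interview and follow-ups at 2 and 5 weeks. It makes no separate provision for anyone who has been terminated.

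On analysis, the SAP's section on non-adherence and missing data states: "We will perform an intent-to-treat analysis of the data. Subjects will be grouped according to how they are randomized". Missing values are to be multiply imputed in time order; for the second stage, "the imputed and observed values of the first-stage results will be used in conjunction with baseline variables to impute" what is missing. The same section adds: "We will examine the distribution of missing data according to intervention groups, covariates (e.g., demographic characteristics, adherence, reason for discontinuation".

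**The concern.** Worsening is a legitimate safety ground. Non-response is different, because it is close to what the trial measures. The design also needs non-responders: Aim 1 compares "referral vs CD among testing decliners" (CD is critical dialogue), and section 6 of the protocol samples 35 people who did not complete testing for interview. A rule that can take unresponsive people out of the study works against that purpose.

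If termination ends data collection, the missing outcomes are missing for a reason related to the outcome. Arm-level uptake or adherence can then be overstated. If termination differs between arms, a comparison can be biased in either direction.

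**Working it through.** **What the text settles.** The action is removal from the study. The general schedule does not say that follow-up continues after removal. Intent-to-treat grouping fixes the arm a person is counted in, not whether the outcome is observed. Imputation from baseline and first-stage results covers removals that those results explain. The remaining exposure is removal after the first-stage results because of second-stage non-response or worsening that is not in the data.

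**Inputs from the documents.** 670 recruited, 15% attrition, 582 final (protocol section 4); interviews at 2 and 5 weeks (section 8); $40 per follow-up interview (section 6). Checking the plan's own figure: 582 × 1.15 = 669.3, which rounds up to 670, whereas 670 × 0.85 = 569.5. So 670 is 582 raised by 15%. Nothing below depends on that difference.

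**Assumptions, not in the documents.** Half of the 582 decline testing and split evenly between CD and referral: 582/4 = 145.5, simulated as 145 per arm. True second-stage uptake p is 25% or 40%, with no true difference between arms. Would-be non-responders are removed at rate t and would-be responders at r × t. Removed outcomes are imputed at the rate of those who stay in the arm.

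**Formulas.** Rate among those who stay = p(1 − rt) / [p(1 − rt) + (1 − p)(1 − t)]. The odds in an arm are therefore multiplied by (1 − rt)/(1 − t), whatever p is.

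Example, r = 0.5, t = 20%:
- p = 25%: 0.225 / (0.225 + 0.600) = 27.3%, which is 2.27 points too high.
- p = 40%: 0.36 / (0.36 + 0.48) = 42.9%, which is 2.86 points too high.
- Odds multiplier: 0.90/0.80 = 1.125.

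Type I error comes from a two-proportion z-test on retained participants, 400,000 runs, nominal 5%. Paired values are for p = 25% and p = 40%.

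| Removal pattern | False difference (points) | False odds ratio | Type I error |
|---|---|---|---|
| One arm, r = 0.5, t = 6.9% | 0.69; 0.88 | 1.037 | 5.30%; 5.35% |
| One arm, r = 0.5, t = 10% | 1.03; 1.30 | 1.056 | 5.44%; 5.58% |
| One arm, r = 0.5, t = 20% | 2.27; 2.86 | 1.125 | 7.12%; 7.66% |
| 20% vs 10%, r = 0.5 | 1.25; 1.55 | 1.066 | 5.63%; 5.79% |
| Both arms 20%, r = 0.5 | 0 | 1.000 | 5.09%; 5.05% |
| One arm, t = 20%, unrelated to outcome (r = 1) | 0 | 1.000 | 5.04%; 5.02% |
| Extreme: one arm, t = 20%, only non-responders (r = 0) | 4.41; 5.45 | 1.250 | 12.8%; 15.0% |

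**Where 6.9% comes from.** If bi-monthly means every two months, reviews are about 8.7 weeks apart, and the gap between the two interviews is 3 weeks: 3/8.7 = 34.5% of participants have a review in that gap. If 20% of the non-responders reviewed are removed, 0.20 × 0.345 = 6.9%. If bi-monthly means twice a month, this limit does not apply.

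**First-stage comparison.** Assume stage-one uptake of 55% with navigation services and 45% with the brochure. The difference in final testing is 10 × (1 − p) points. With t = 20% and r = 0.5 in both decliner arms, it shrinks from 10 × 0.75 = 7.5 to 10 × 0.727 = 7.3, or from 10 × 0.60 = 6.0 to 10 × 0.571 = 5.7.

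**The case against.** The strongest reply is that the damaging route is inferred. The interim review works from data, so someone identified there as unresponsive has usually been identified from recorded results. If the record is the 5-week outcome, nothing is lost; if it is a first-stage or 2-week result, imputation can use it. Harm needs removal between weeks 2 and 5 on information outside the dataset. That narrows the problem but does not close it: staff reports of worsening are one such source, and the text does not exclude them.

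The clause is also discretionary, sits in a safety paragraph and may rarely be used. Nothing suggests that its use would differ by arm. The imputation sentence is offered as an example, and the plan already intends to examine missingness by reason for discontinuation. The default schedule covers every participant, and provisions on withdrawal may sit in text not available here. All of this stands and keeps the rating low. However, examining missingness does not recover an outcome, and the plan states no sensitivity analysis for departures from missing at random.

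The numbers have limits too. Every removal rate is assumed. The simulation tests retained participants instead of running the planned imputation, and it applies removal to a total already net of attrition. The one case tied to the visit schedule gives a type I error of about 5.3%, which is practically nominal. The extreme row needs foresight that a sub-committee would not have and should carry little weight.

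**Conclusion.** The point holds, as a minor one. The text permits removal from the study on outcome-related grounds, and no text available preserves the outcomes of those removed. With one-arm removal at t = 6.9% to 20% and r = 0.5, the false CD–referral difference is 0.7 to 2.9 points and type I error 5.3% to 7.7%. With equal t and r in both arms the odds multipliers cancel, leaving overstated arm-level rates and a slightly smaller navigation–brochure difference. If removal is unrelated to the outcome, there is no bias. The documents give no termination count, so the actual size cannot be determined. Confidence is medium, because the absence of a follow-up provision could be confirmed only in the text available.

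**What to change.** Reword the clause so that the review may lead to stopping the intervention and referring the participant for care, while the 2- and 5-week interviews and test status are still collected unless the participant withdraws consent, and the participant is analysed as randomized. Record the arm and reason for each such decision, so that the planned look at missingness by reason for discontinuation has data to use. The care decision is unaffected. If collection has already closed (section 2 of the protocol gives an end date of 05/12/2022), report terminations by arm and reason.

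The cost is one or two sentences, minor logging and a few interviews already scheduled. With r = 0.5, p = 25% and one remaining $40 interview each:
- t = 6.9% in both arms: 2 × 145 × (0.069 × 0.75 + 0.0345 × 0.25) = 17.5, so 18 people and $720.
- t = 20% in both arms: 2 × 145 × (0.20 × 0.75 + 0.10 × 0.25) = 50.75, so 51 people and $2,040.

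Both sums fall within the payments already planned for 670 participants.

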## **Methods for additional analyses (e.g., subgroup analyses)**

Aim 2: To identify other predictors of these outcomes, we will include these variables as covariates using logistic regression analysis. We will model probabilities of testing behavior (completed vs testing decliners) and adherence to NJ recommendations as functions of the first-stage intervention and other covariates in the logistic regression analysis.

**Qualitative component analysis:** Critical dialog sessions and in-depth interviews will be digitally audio-recorded and transcribed. Data will be entered into Atlas.ti, a qualitative data processing program. Analysis rooted in phenomenology and grounded theory will include continuous coding, comparison, and recoding to yield categories and connect experiences and themes. The analysis will focus on participant reports about their experiences with the intervention, barriers to testing and adherence to NJ recommendations, and suggestions on how to address these barriers.

**Methods in analysis to handle protocol non-adherence and any statistical methods to handle missing data**

We will perform an intent-to-treat analysis of the data. Subjects will be grouped according to how they are randomized. The multiple imputation strategy described will be adapted [43]. This uses a time-ordered nested conditional imputation strategy with multiple imputation of missing values. In this approach, the fully conditional specification (FCS) imputation framework wherein a separate model for each variable is fitted will be applied. We will consider the time ordering of the data. For example, observed baseline variables will be used to impute for missing data from the first-stage results. Then, the imputed and observed values of the first-stage results will be used in conjunction with baseline variables to impute missing values for the second-stage results. We will examine the distribution of missing data according to intervention groups, covariates (e.g., demographic characteristics, adherence, reason for discontinuation), outcome variables, and time. We will determine whether the missing data pattern is not inconsistent with the missing-at-random (MAR) mechanism. We will also check whether the amount of missingness is monotonic over time. The R software packages mice and pan will be used for imputation.
